#### 7.2.4 Foreseeable adverse events and anticipated adverse device effects

The following adverse events are outlined in the device's Instructions for Use:

Infection, increased chronic inflammation, allergic reaction, unexplained fever or chills, excessive redness, acute and chronic pain, swelling, tender scars, adhesions, seroma formation, fistula formation, hematoma, recurrence of tissue defect, anastomotic stricture formation and leaks, dyspareunia, vaginal shortening, vaginal bleeding, atypical vaginal discharge, groin and/or buttock and/or leg pain, urinary or fecal incontinence, delayed or failed incorporation of graft, failure to repair a prolapse, recurrent prolapse, mesh or suture erosion or extrusion, and injury to the bladder, bowel, blood vessels, and/or nerves of the pelvis.

# 7.3 Reporting Requirements

#### 7.3.1 Reporting of AEs and SAEs

The investigator will determine if there has been a potentially device or procedure related adverse event or potentially device or procedure related serious adverse event. All potentially device or procedure related adverse events and potentially device or procedure related serious adverse events must be reported on the "Adverse event" form of the eCRF.

Potentially device or procedure related adverse events and potentially device or procedure related serious adverse events will be evaluated and differentiated by:

- Seriousness of the event;
- Causality of the event (in relation to the device or procedure);
- Severity of the event.

All potentially device or procedure related AEs and potentially device or procedure related SAEs must be collected for all enrolled subjects starting from the time of enrollment through the last Follow-up. Each AE must be described as follows:

AE Term: A medically defined diagnosis/symptom. Use the highest level of evidence available.

Level 1: Diagnosis (highest level)

T-GENVIH-002 study

Confidential

Level 2: Symptoms

Level 3: Signs (lower level)

**AE Description:** Explain the circumstance of becoming aware of the event, how the subject explained the circumstances surrounding the onset of the event, the underlying cause (the diagnosis), coexisting disease, or other condition or complaint involving the event.

**AE Duration**: Document by entering the date of onset (start date) and date of resolution (stop date).

**AE Causality:** Document causal relationship between event and the investigational product and Study Procedure (related, possible, probably, not related,).

AE Seriousness: Document as serious or not serious

**AE Severity**: Document as mild (transient and easily tolerated by the subject), moderate (discomfort and interrupts normal activities), or severe (incapacitating with inability to work or do usual activity)

**Action(s) Taken and/or Treatment(s)**: Document as none, medication, hospitalization, surgical, and/or other. Any prescribed medication should be noted in the subject's medical records and transcribed onto the AE and Concomitant Medications CRFs. If a surgical or invasive procedure is required for an AE, document the procedure on the Invasive Procedure Log.

**Outcome**: Document as recovered without sequelae, recovered with sequelae, ongoing, death, or other. AEs will be followed until a resolution has occurred, until a resolution is no longer expected, the pre-existing condition returns to baseline conditions, or the subject exits the study.

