#### 5.4 Point of Enrollment & Enrollment Period

There are no physical participants as this is a retrospective study. The requirement for consent being waived, the patients will not provide informed consent to allow use of their data. There is no traditional enrollment period in this study. Data will begin to be collected from the first patient who meets all the eligibility criteria.

This study is anticipated to have a data collection period of one month from initiation of the site until data delivery.

The total expected duration of the study is, therefore, approximately 3 months.

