## 6.1.2 Index Surgery

The patients' data to be collected at the index surgery are:

- Ventral Hernia Details: Location and size of the ventral hernia(s), CDC Wound Class (the highest one) and complications associated with Hernia(s) repair.
- Surgery Details: Surgical approach (Robotic, Laparoscopic, Robotic assisted, Laparoscopic assisted, MIS converted to open, Open), Times related to the different steps of the index surgery.
- Type of the Gentrix Surgical Matrix Used.

- Intraoperative Details: Surgical Plane of graft placement, Graft fixation, Component separation,
   Concomitant procedure, Stoma presence, and Fascial closure.
- Adverse Events: Information will be collected on any adverse event that the subject is experiencing during or after the surgical procedure.
- Device Deficiency: Medical records will be reviewed for DDs that were documented during the timeframe of treatment with the subject device.

Note: Completion of Worksheets/ eCRFs: Site will transcribe/transmit the above-mentioned patients' data in study worksheets & eCRFs. The patients' data will originate from existing medical and other patient records.

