# 6.3 Monitoring

Clinical site monitoring is conducted to ensure that the rights and well-being of trial participants are protected, that the reported trial data are accurate, complete, and verifiable, and that the conduct of the trial is in compliance with the currently approved protocol, with International Conference on Harmonisation Good Clinical Practice (ICH GCP), and with applicable regulatory requirement(s).

Authorized, qualified clinical research associate (CRA) of Integra LifeSciences will accomplish the monitoring of the collected retrospective data per the study specific clinical monitoring plan.

The investigator and study staff will allocate adequate time for such monitoring activities. The investigator will also ensure that the monitor or other compliance or quality assurance reviewer is given access to all the study-related documents. The site will participate in an initiation visit and will be trained on the study protocol, the eCRF and study related responsibilities. One on-site visit will occur once the study site has completed the eCRFs, so that the Clinical research Associate from Integra LifeSciences can verify the collected data to the source documents (100% source data verification).

The onsite Close-Out Visit may be a combined visit with the monitoring visit.

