## 7.2 Reporting of Safety Information

## 7.2.1 Non-Reportable Event

All Adverse Events, related or not related to the study device or study index procedure by the investigator, are required to be reported in this study.

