#### 7.2.3 Causality

The relationship between the use of the medical device (including the medical - surgical procedure) and the occurrence of each adverse event shall be assessed and categorized.

Each AE will be classified according to four (4) different levels of causality:

**Not related**: Relationship to the device, or procedures can be excluded when:

- the event has no temporal relationship with the use of the study devices, or the procedures related to application of the study devices;
- the serious adverse event does not follow a known response pattern to the medical device (if the response pattern is previously known) and is biologically implausible;
- the discontinuation of medical device application or the reduction of the level of activation/exposure when clinically feasible and reintroduction of its use (or increase of the level of activation/exposure), do not impact on the serious adverse event;
- the event involves a body-site or an organ that cannot be affected by the device or procedure;
- the serious adverse event can be attributed to another cause (e.g., an underlying or concurrent illness/ clinical condition, an effect of another device, drug, treatment or other risk factors);
- the event does not depend on a false result given by the investigational device used for diagnosis, when applicable;

In order to establish the non-relatedness, not all the criteria listed above might be met at the same time, depending on the type of device/procedures and the serious adverse event

**Possible:** The relationship with the use of the investigational device or comparator, or the relationship with procedures, is weak but cannot be ruled out completely. Alternative causes are also possible (e.g., an underlying or concurrent illness/ clinical condition or/and an effect of another device, drug or treatment). Cases where relatedness cannot be assessed, or no information has been obtained should also be classified as possible.

**Probable:** The relationship with the use of the investigational device or comparator, or the relationship with procedures, seems relevant and/or the event cannot be reasonably explained by another cause.

**Causal relationship:** the serious adverse event is associated with the investigational device, or with procedures beyond reasonable doubt when:

- the event is a known side effect of the product category the device belongs to or of similar devices and procedures;

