#### 7.3.3 Regulatory Reporting and Timelines

Report by the Investigator to the Sponsor

The sponsor shall implement and maintain a system to ensure that the reporting of the reportable events as defined under Section 7.2.1 Non-Reportable Event will be provided by the investigator to the sponsor immediately, but not later than 5 calendar days after investigation site study personnel's awareness of the event.

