#### 5. STUDY PROCEDURE

This retrospective study specifically aims to collect data from the day of the index procedure, and post-operatively up to a maximum of one year or shorter as applicable. Data will be collected via medical records, study worksheets, and entered into electronic data capture system by the site.

Enrollment period will be approximately 1 month. Total duration of the study will be approximately three months.

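### Protocol 7.3.1 directs AE-form entry to potentially device- or procedure-related events from enrollment, while the rest of the plan covers all AEs from the index procedure; a site that applies 7.3.1 as its entry rule would leave the AE tables incomplete

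*Protocol*

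**What the plan says.** Protocol 7.3.1 applies the qualifier of potential relatedness to device or procedure at each step: what the investigator determines, what must go on the AE form of the eCRF, what is evaluated, and what is collected. On collection it says "potentially device or procedure related SAEs must be collected for all enrolled subjects starting from the time of enrollment through the last Follow-up", with AEs named in the same sentence.

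Other sections are wider:

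- Protocol 7.2.1, despite a title that suggests exclusions, says: "All Adverse Events, related or not related to the study device or study index procedure by the investigator, are required to be reported".
- Protocol 7.3.3 sets its clock on that wider set. The reporting of events "defined under Section 7.2.1 Non-Reportable Event will be provided by the investigator to the sponsor immediately, but not later than 5 calendar days" after site staff become aware of them.
- Protocol 6.1.2 says "Information will be collected on any adverse event that the subject is experiencing during or after the surgical procedure". Sections 6.1.3 and 6.1.4 repeat this for discharge and follow-up. Each of the three ends with a note that the site transfers the listed data to worksheets and eCRFs.
- Protocol 9.2 has AEs entered in the EDC system with no limit on relatedness.
- Protocol 7.2.3 says "Each AE will be classified according to four (4) different levels of causality", and one of the four is not related.

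On timing, protocol 5.4 says "There is no traditional enrollment period in this study", while SAP section 5 says "Enrollment period will be approximately 1 month". The synopsis and SAP section 5 both give a data window that opens on the day of the index procedure and closes at one year at most.

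**The concern.** The narrower rule sits in the section that names the AE form. A site could reasonably abstract charts by it and leave out events it judges unrelated. The planned outputs need those events. Protocol 10.4.6 counts subjects with any AE beside subjects with any related AE, and SAP 9.3.5 tabulates AEs and SAEs by relationship to device and to procedure. If relatedness decides entry, the first contrast shrinks and the not-related cells are short. Unrelated deaths and SAEs could also be absent from the listings. The aim in protocol 3.1 of finding unknown side effects would then rest on a relatedness judgement made before the event is recorded.

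The start point is a second mismatch. In a chart review the surgery precedes data collection, by at least 90 days under inclusion criterion 1. Enrollment is therefore a poor marker for AE onset.

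**Working it through.** No sample-size, power or alpha figure is involved, so the check compares the texts.

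**1. Scope.** Take an AE that the investigator is confident is unrelated to both device and procedure.

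- Under 7.2.1 it must be reported.
- Under 7.3.3 it must reach the sponsor within 5 calendar days of awareness.
- Under 6.1.2 to 6.1.4 it is collected and transferred to the eCRF, and under 9.2 it is entered in the EDC system.
- Under 7.2.3 it receives a causality level.
- Under 7.3.1 it is outside the set that must go on the AE form.

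No section gives one rule precedence. Section 7.3.1 does not say that other events are excluded, and its own causality field offers not related as a value. That value does not settle the matter, because it could also describe an event related to the procedure but not to the device.

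**2. Start point.** Sections 7.3.1 and 7.3.2 start at enrollment. The synopsis, SAP section 5 and the AE items in 6.1.2 to 6.1.4 start at the index procedure. For device deficiencies, 6.1.2 refers to the period of treatment with the device, and Table 1 marks index surgery only.

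**3. Outputs at risk if 7.3.1 is used as the entry rule.**

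- Incomplete: the any-AE count and the AE tables by system organ class and preferred term (protocol 10.4.6); the not-related cells (SAP 9.3.5); and the listing of unrelated SAEs and deaths.
- Not affected by the relatedness limit: the any-related-AE count and the tables of device effects.
- Not affected: the primary and secondary complication endpoints, which protocol 6.1.3 and 6.1.4 and SAP 9.2.6 list as data items apart from AEs.

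**4. Scale.** The planned size is about 35 treated subjects (protocol 10.2, SAP section 8). Each subject whose only AE is unrelated and not entered lowers the any-AE percentage by 1/35 = 2.9 percentage points. The number of such subjects is unknown, because the documents give no rate of unrelated AEs and no share that would go unentered.

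**5. Coding.** Protocol 10.4.6 codes all AEs in MedDRA. SAP 9.3.5 names only adverse device events for MedDRA coding, although it also relates AE verbatim terms to body systems.

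**The case against.** The strongest reply is that a site can satisfy every section at once by entering all AEs. Section 7.3.1 never says only, the visit sections carry their own eCRF-entry instruction, and 9.2 has no relatedness filter. Protocol 5.5 asks for any SAE even in screen failures. Events whose relatedness cannot be assessed default to possible under 7.2.3. This stands, and it makes the loss conditional. It does not remove the conflict: the default does not cover events confidently judged unrelated. Section 7.2.3 also classes complications of routine procedures not imposed by the plan as not related, and that class may be wide in a retrospective study.

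Monitoring is a further safeguard. Protocol 6.3 aims at complete data, trains the site on the protocol and eCRF, and has a monitor who "can verify the collected data to the source documents (100% source data verification" at an on-site visit. That should catch some omissions. The check is worded around data already collected, however, and the monitor would have the same two rules to apply to an event that was not entered.

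A reader might also infer that SAP 9.3.5 fails to list SAEs because its dedicated listing is for serious device effects. That goes too far: its AE listing carries a seriousness field, so SAEs are identifiable there.

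**Conclusion.** The conflict is real and should be fixed. It is one of wording, and its effect is limited to AE safety reporting in a descriptive study. The conclusion that tables would be incomplete assumes that the site treats 7.3.1 as an exclusive entry rule, which most of the protocol argues against.

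Three stronger readings are tempting and are not supported:

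- That 7.3.1 alone governs what reaches the eCRF. Sections 6.1.2 to 6.1.4 and 9.2 also instruct entry.
- That the plan gives no usable date to bound AE onset. The synopsis and SAP section 5 give one, from the day of the index procedure to at most one year. The fault is that 7.3.1 and 7.3.2 do not use it.
- That the loss of ability to detect an unsuspected event can be quantified. Any such figure would need an assumed event risk and an assumed share of unentered events, and the documents supply neither.

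**What to change.** Reword protocol 7.3.1 so that all AEs and SAEs, whatever their relatedness, with onset from the day of the index procedure through last follow-up (one year at most) are recorded on the AE form. Keep relatedness as a field on that form and do not use it to decide entry.

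Two consequential edits follow. In protocol 7.3.2, replace the enrollment start for device deficiencies and reconcile the section with 6.1.2 and Table 1. In SAP 9.3.5, MedDRA-code all AEs, as protocol 10.4.6 does.

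The cost is a short protocol amendment, with the written concurrences that protocol 11.2 requires, and a small SAP edit. Chart abstraction does not grow beyond what 7.2.1 already demands at the single site.

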# 7.2.2 Severity

Each adverse event will be classified according to three (3) levels of severity. The Sponsor and the investigator will use the following definitions to assess the severity of the adverse event:

**Mild** – Awareness of signs or symptoms, but easily tolerated and are of minor irritant type causing no loss of time from normal activities. Symptoms do not require therapy or a medical evaluation; signs and symptoms are transient.

**Moderate** – Events introduce a low level of inconvenience or concern to the participant and may interfere with daily activities, but are usually improved by simple therapeutic measures; moderate experiences may cause some interference with functioning

**Severe** – Events interrupt the participant's normal daily activities and generally require systemic drug therapy or other treatment; they are usually incapacitating

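### Protocol 7.2.2 and 7.3.1 set different AE severity scales, and 7.3.1 asks for fewer AEs than 7.2.1, so the descriptive AE tables can depend on which section the site follows

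*Protocol*

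**What the plan says.** **Severity.** Protocol 7.2.2 introduces a three-level scale with "The Sponsor and the investigator will use the following definitions to assess the severity of the adverse event". Its Mild level includes the condition "Symptoms do not require therapy or a medical evaluation; signs and symptoms are transient". Its Severe level reads "Events interrupt the participant's normal daily activities and generally require systemic drug therapy or other treatment; they are usually incapacitating". Its Moderate level covers low inconvenience that may interfere with daily life and usually improves with simple measures.

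Protocol 7.3.1, which lists what to record for each AE, gives its own short definitions: "mild (transient and easily tolerated by the subject", then "moderate (discomfort and interrupts normal activities), or severe (incapacitating with inability to work or do usual activity". It does not refer to 7.2.2.

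**Capture.** Protocol 7.2.1 says "All Adverse Events, related or not related to the study device or study index procedure by the investigator, are required to be reported". Protocol 6.1.2 says "Information will be collected on any adverse event that the subject is experiencing during or after the surgical procedure", and 6.1.3 and 6.1.4 repeat this for discharge and follow-up. Protocol 7.3.3 relies on 7.2.1: "reportable events as defined under Section 7.2.1 Non-Reportable Event will be provided by the investigator to the sponsor". Protocol 7.3.1 states its requirement once for the AE form and once for collection, and both times limits it to events potentially related to the device or procedure. Its causality field nevertheless offers a not-related option.

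**Use in the analysis.** SAP 9.3.5 tabulates AEs and serious AEs by severity and by relationship to device and procedure. Protocol 10.4.6 counts subjects with any AE and, separately, subjects with any related AE.

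**The concern.** Both severity scales are written as instructions, and neither document says which governs. The same charted event can therefore sit in different rows of the SAP 9.3.5 severity table with no error by the site.

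The capture wording raises a second problem. Protocol 10.4.6 needs unrelated AEs for its any-AE row, yet the instructions tied to the AE form do not ask for them. Protocol 3.1 says the study will also look for side effects not yet known. An event judged unrelated and never entered cannot be re-examined from the database.

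**Working it through.** The plan gives no figure to reproduce and the study tests no hypothesis (Protocol 10.1), so the check is a comparison of texts.

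**Step 1: severity, by type of event**

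| Event | Under 7.2.2 | Under 7.3.1 |
|---|---|---|
| A. Interrupts normal activity, was treated, not incapacitating | Severe: interruption and treatment both match, and incapacity is only usual | Moderate: interruption matches, and Severe needs incapacity |
| B. Transient and easily tolerated, but needed therapy or medical evaluation | Not Mild; Moderate is the next level | Mild: there is no therapy or evaluation test |
| C. Interrupts normal activity, untreated, not incapacitating | Moderate is arguable | Moderate |
| D. Incapacitating, unable to work | Severe | Severe |

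The scales part on A and B, and 7.3.1 gives the lower grade in both. C and D show that the conflict does not reach every event. B matters in a chart review because treatment and evaluation are among the facts a record is likely to show.

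**Step 2: capture, by type of event**

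| Event | 7.2.1, 6.1, 7.3.3 | The two 7.3.1 sentences |
|---|---|---|
| Judged potentially related | Required | Required |
| Relatedness uncertain or not assessable | Required | Required, because 7.2.3 classes these as possible |
| Judged clearly unrelated | Required | Neither required nor barred |

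Only the last row differs. If such events are left off the form:
- the any-AE row in Protocol 10.4.6 loses subjects whose only AEs are of this kind;
- the preferred-term counts there and the not-related cells of SAP 9.3.5 are short;
- the any-related-AE row does not change.

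**Step 3: size per subject**

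The planned sample is about 35 treated subjects (Protocol 10.2, SAP 8). One subject shifts a row by 100/n percentage points:
- n = 35: 100/35 = 2.9
- n = 30: 100/30 = 3.3
- n = 40: 100/40 = 2.5

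The bounds of 30 and 40 are my assumption for approximately 35. The documents give no expected AE counts, so a total shift cannot be calculated. Protocol 10.4.6 tabulates repeats of the same AE at the greatest severity. Where that rule applies, regrading one occurrence moves a row only if the subject's greatest grade changes. SAP 9.3.5 does not state the rule.

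**The case against.** The strongest reply is that the capture question is already settled. Protocol 7.2.1, 6.1.2 to 6.1.4, 7.3.3 and 10.4.6 all point to every AE, and so does the not-related option in 7.3.1. Entering every AE satisfies every section, while entering only related ones breaches 7.2.1. Protocol 6.3 and 9.1 also provide for full source data verification. Most of this stands, and it makes the capture point the softer of the two. A reader might infer that 7.3.1 restricts the database to related AEs; it does not, because it states a minimum and excludes nothing. What remains is that the sentences governing the form ask for less than 7.2.1. Verification may catch some omissions, but it does not decide which scope applies.

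On severity, the reply is that Severe in 7.2.2 also speaks of treatment and usual incapacity, so an untreated event that is not incapacitating could be Moderate in both places. That is right, and it is case C. The reading that every activity-interrupting event changes grade is therefore too strong. Cases A and B remain.

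A reader might also infer that the loose use of procedure in 7.2.3 leaves the procedure-related category empty, since a chart review imposes no procedure. The text does not support that: 7.2.3 opens by including the surgical procedure, and 7.2.1 names the index procedure.

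**Conclusion.** The point holds as a conflict between stated rules: firmly for severity, more weakly for capture. It should be corrected, but it does not threaten the main results.

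A reader might infer that the primary endpoint is affected. The documents do not support this. No primary or secondary endpoint is defined by AE severity grade or AE causality category, although reoperation carries its own attribution to the index repair. SAP 9.3 takes the endpoints from the surgery, discharge and follow-up reports. The study has one arm and one site, so there is no comparison to bias. The effect is confined to the descriptive AE tables.

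The size is 2.9 percentage points per affected subject at n = 35 (2.5 to 3.3 for the assumed 40 to 30), and the number affected is unknown. The SAP 9.3.5 listing will show the grade and relationship given to each recorded event. It cannot show which scale was used or which events were never entered. All this assumes that the eCRF, which is not in the documents, does not already impose one scale and one scope.

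**What to change.** 1. Remove the short severity definitions from Protocol 7.3.1, and have 7.3.1 and SAP 9.3.5 refer to 7.2.2, which already binds both sponsor and investigator.
2. Reword the two 7.3.1 sentences, on the AE form and on collection, to the all-AE scope of 7.2.1.
3. Check that the severity field and AE form instructions in the eCRF match.
4. If forms are already complete, state in the report which severity scale and which capture scope the site used.

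The cost is a small protocol amendment, which under Protocol 11.2 needs written agreement from the sponsor, the ethics committee and any applicable authorities, plus a short SAP edit. The site must enter unrelated AEs on the form, although 7.2.1 already requires them to be reported. The stricter Mild definition in 7.2.2 may move some charted events from Mild to Moderate.
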